The three co-primary endpoints for this study are:

- a. ASES score at 22+ Months
- b. No unanticipated device-related adverse event, and no fracture, perforation of the bone or joint dislocation, and no fracture, perforation or dissociation of the device, and no revision or removal of any component, and
- c. Radiographic Success, as defined by:
 - a. Subsidence of the humeral component < 5 mm, and
 - b. Migration of the humeral component < 5mm, and
 - c. No progressive lucency around the humeral component >2mm in two or more contiguous zones
 - d. Migration of the glenoid component <5 mm, and
 - e. No progressive lucency >2mm around the entire glenoid component

SECONDARY ENDPOINTS

The data collected will also be analyzed for the following secondary endpoints:

- 1. American Shoulder and Elbow Surgeon's Score (ASES) at all time points
- 2. Single Assessment Numeric Evaluation (SANE) Score at all time points
- 3. Constant Score at all time points, except 6 weeks (adjusted for age and gender)
- 4. Radiographic assessment of radiolucencies and subsidence
- 5. Overall adverse events including removal/revision and other serious adverse events

The safety of the system will be monitored by recording adverse events including serious adverse events not considered UADEs throughout the follow-up period. Types of events to be collected include but are not limited to:

- Device removal or revisions
- Unanticipated adverse device events
- Systemic adverse events
- Local adverse events
- Reoperations and Other Interventions

Study participants will only be considered discontinued/withdrawn for the following reasons:

- Death
- Withdrawal of consent (written)
- Revision/Removal

Information from any patient who fails to return for multiple, consecutive, scheduled follow-up visits for any reason other than the criteria listed above will be identified as Missing Data.

ANTICIPATED CHANGES

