A description of all protocol deviations will be provided. The association between the proportion of subjects with a protocol deviation and device group across investigators will be examined using the Breslow-Day test for homogeneity of odds ratios. Investigators with less than or equal to 3 cases in either treatment will be combined to form a "pooled" investigator for analysis. A significant p-value indicates heterogeneity of odds ratios for the proportion of subjects (Investigational vs Control) with a protocol deviation across investigators, and in this case the proportions of subjects with a deviation will be examined graphically and descriptively by treatment group and site to assess dependency.

DATA COLLECTION

DATA COLLECTION TIME POINTS

Windows for this study will be as follows:

Table 1: Analysis Windows

Interval	Follow-Up Window
	(Days from Surgery)
Preoperative	≤ 0
6 Weeks	28-56
3 Months	78-106
1 Year	304-426
2 Year	669-791
2+ Year	> 791

The principal data collected is described in the following table:

Study Parameter	Data Collected
Demographic and Baseline Measurements	Age, Height, Weight, Gender, Race/Ethnicity, Unilateral/Bilateral, Primary Diagnosis, Prior Treatments, Concomitant Medications
Efficacy Measurements	American Shoulder and Elbow Surgeons (ASES) Score, Constant Score, SANE Score, Radiographic Assessment
Safety Measurements	Revision/Removal, Adverse Events
Study Success Criteria	Study success requires that the Investigational group successfully demonstrate non-inferiority when compared to the Control group for all three of the individual primary endpoints.

Table 2: Principal Study Data

INFERENTIAL METHODS

SIGNIFICANCE LEVELS

The Type I error rate for the primary study analysis will be 0.05.

Comparisons for secondary, exploratory, and safety analyses will use $\alpha = 0.05$, with no adjustment for multiple comparisons. Because no adjustments will be made for multiple

comparisons, secondary, exploratory, and safety endpoints will be reported as exploratory analyses without claims of statistical significance.

SUBJECT ACCOUNTING

Accountability tables will be generated to show, at each study visit, the number of Investigational and Control subjects who might be expected to attend a given visit and the number and proportion who did attend.

The following definitions specify how the subject accountability table tracks subject follow-up for the Control and Investigational arms:

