Theoretically Due: The number of implants that could be examined if all subjects returned on the first day of the follow-up window based on their respective initial surgery dates and the date of database closure.

Deaths: The number of deaths that have taken place in the course of the investigation according to scheduled follow-up visits.

Revisions: The number of revisions that have taken place in the course of the investigational study recorded according to the scheduled follow-up visit.

Withdrawal of Consent: The number of subjects that have withdrawn during the course of the investigational study recorded according to the scheduled follow-up visit.

Not Yet Overdue: Subjects in this category are those who have not yet been evaluated but who are still within the evaluation time window at the time of database closure.

Actual^A: The number of subjects with complete data (i.e. all primary outcomes can be determined) who are actually evaluated within the protocol-defined follow-up intervals.

Actual^B: The number of subjects with any follow-up data (in- or out-of-window) reviewed or evaluated by investigator ("all evaluated" accounting).

Expected: This element is the number of subjects expected for a given time interval. These include the theoretical number of subjects who are due to be evaluated, less the number of subjects who have died, withdrawn, been revised, or are not yet overdue in this time interval.

Follow-up Rate: This element is the ratio of actual subjects evaluated to expected subjects, expressed as a percentage.

MODELS FOR CONTINUOUS MEASURES

Comparisons of Investigational vs Control with regard to continuous baseline and secondary outcomes will be performed using standard statistical tests and will be chosen as appropriate for the scale and distribution of the measures being analyzed. A t-test, Wilcoxon test, or oneway ANOVA (as appropriate) will be performed to assess differences.

CATEGORICAL DATA ANALYSES

Comparisons of Investigational vs Control with regard to categorical baseline, secondary and safety outcomes will be performed using standard statistical tests and will be chosen as appropriate for the scale and distribution of the measures being analyzed. Specifically, categorical outcomes will be compared for investigational and control groups using the Fisher's Exact test (for 2x2 tables) or the Likelihood Ratio chi-square test (for tables larger than 2x2).

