BASELINE CHARACTERISTICS

Subjects in the Investigational and Control study groups will be compared regarding a list of baseline items, including preoperative ASES and Constant Scores, demographics (age, gender, and primary diagnosis), medical history, and comorbidities.

EFFICACY EVALUATIONS

Primary Endpoint

The confidence intervals used in the analysis of the binary primary endpoints (Radiographic Success and Absence of Revision/Removal/UADE) will be 1-sided, 95% confidence intervals for the difference between proportions in two independent samples. They will be calculated using the Wald method as based on a normal approximation to the binomial, as follows:

$$(p_C - p_I) + z_\alpha \sqrt{SE_C^2 + SE_I^2}$$

Where

 p_{C} = proportion of success in the Control group, p_{I} = proportion of success in the Investigational group, α = 0.05, and

$$SE_C = \sqrt{\frac{p_C(1-p_C)}{n_C}}$$
 and $SE_I = \sqrt{\frac{p_I(1-p_I)}{n_I}}$

The confidence interval used in the analysis of the continuous primary endpoint (ASES Score) will be a 95% confidence interval for the difference between means in two independent samples. They will be calculated using the normal distribution, as follows:

$$(\overline{x}_C - \overline{x}_I) + z_\alpha \sqrt{\frac{s_C^2}{n_C} + \frac{s_I^2}{n_I}}$$

Where

 x_{C} = mean ASES score in the Control group,

 $\overline{x_{I}}$ = mean ASES score in the Investigational group,

 $s_{\scriptscriptstyle C}$ = standard deviation of the ASES scores for the Control group,

 s_{T} = standard deviation of the ASES scores for the Investigational group, and

 $\alpha = 0.05$

Secondary Endpoints

Secondary outcomes include the ASES score, SANE score, Constant score, and radiographic endpoints at 6 weeks, 6 months, 1 year, and 2 years separately. These outcomes will be compared for Investigational and Control groups at each time point.

Exploratory Analyses14

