Subject covariates in the proposed statistical modeling below include treatment group, age at time of surgery, gender, BMI, primary diagnosis, and preoperative ASES score. Others may be added if other covariates potentially affecting the outcome become apparent. To determine the effect of these covariates on the primary endpoints, separate regression models will be used. In the regression models, the dependent variable will be the primary study endpoint; thus a logistic regression model will be needed for the binary study endpoints. The baseline and demographic variables listed above will be independent variables. A graphical examination of the residuals will be performed to assess the model assumptions. To determine whether a covariate has an effect on the primary study outcome, a Type 3 analysis of effects based on the Wald Chi-square test will be conducted.

In addition, the time to revision will be calculated for each subject in the investigative and control groups. For those individuals that do not experience a revision, their outcome will be classified as censored. Failure-free curves will summarize and illustrate the proportion of endpoint-free subjects for the Investigational and Control groups over the course of the study. The Kaplan-Meier product-limit method will be used to construct the endpoint-free curves for the Investigational and Control groups.

Also, a proportional hazards regression model will be fit to model the time-to-revision and censored data¹⁰. The principle time-to-revision model will include an independent variable for treatment group as well as baseline covariates that may have an effect on survival. The proportional hazards assumption will be assessed graphically and analytically. Once an adequate model has been fit, for the treatment effect and its standard error parameters will be

¹⁴ Exploratory Analyses described will be carried out if possible, depending on the data. If empty cells exist or models do not converge, these analyses will not be performed.

estimated using partial likelihood. If there are a small number of tied event times, exact methods will be used to compute the likelihood; alternatively, Efron's approximation will be used¹¹.

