There is no gender selection criteria prescribed for this investigation. Male and female subject candidates will be solicited for participation in the investigation without bias. The proportion of male to female subjects will be examined to assure that there is no difference between control and investigational groups with respect to this ratio. If an unexpected difference in this ratio exists between control and investigational groups, then a covariate analysis controlling for gender will be performed for the primary analysis of the investigation. This will assure that gender related effects, if they are present, do not bias investigation conclusions.

Conclusion

This clinical investigation will be conducted under a well-defined protocol and subjects will be informed of the potential risks, benefits, and alternate treatments available prior to giving their consent for participation as investigational subjects. Exposure to the investigational device will be determined at random. Subjects' clinical course will be closely monitored and reported on throughout the investigation and new information provided to them that could affect their willingness to participate. The investigational device that will still allow for a valid, scientific analysis of the reported data. The reporting and assessment of all untoward events arising during the course of the investigation will also be required. Therefore, the sponsor believes that all risks that are reasonably foreseeable have been identified and the means for adequately controlling those risks described.

SECTION D: DEVICE DESCRIPTION DEVICE DESIGN AND DESCRIPTION

The Comprehensive[®] Shoulder System with nano humeral component is a humeral prosthesis system intended for use in shoulder replacement surgery. The implant can be utilized for primary shoulder replacement in conjunction with the 510(k) cleared Versa-Dial[™] Humeral Heads (K040610, K060716) and Comprehensive[®] Hybrid Glenoids (K060694). A complete component listing is included in Exhibit 12.

INVESTIGATIONAL DEVICE DESCRIPTION

The subject of this clinical investigation is the Comprehensive[®] Shoulder System with nano humeral component, comprised of the following components:

- A porous-coated stemless humeral component for cementless fixation;
- A polished, modular (2-piece) humeral head for articulation with the glenoid component;
- A molded glenoid component with three peripheral pegs for cemented fixation;

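### The Constant score is listed as adjusted for age and gender, but the SAP neither defines that adjustment nor carries it into the analysis

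*Combined protocol and SAP*

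**What the plan says.** Section B, Secondary Endpoints, lists as its third item "Constant Score at all time points, except 6 weeks (adjusted for age and gender"). ASES and SANE stand beside it without any such qualifier. How the adjustment is to be made is not stated.

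The SAP then treats the score in three places:

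- Efficacy Evaluations, Secondary Endpoints, where the list reads: "Secondary outcomes include the ASES score, SANE score, Constant score, and radiographic endpoints at 6 weeks, 6 months, 1 year, and 2 years separately". The next sentence reads "These outcomes will be compared for Investigational and Control groups at each time point". No adjustment and no covariate is named.
- Models for Continuous Measures, after saying that standard tests will be chosen to suit the scale and distribution: "A t-test, Wilcoxon test, or oneway ANOVA (as appropriate) will be performed to assess differences".
- Baseline Characteristics: the pre-operative Constant score is one of the items on which the arms are compared. The SAP gives it no other use.

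Age and gender do appear as covariates in Exploratory Analyses, but there "In the regression models, the dependent variable will be the primary study endpoint". The same section plans a proportional hazards model for time to revision with baseline covariates. In Section C, under Gender, a "covariate analysis controlling for gender will be performed for the primary analysis of the investigation" is foreseen if the gender ratio differs between the arms. None of these concerns the Constant score.

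Under Significance Levels, secondary comparisons use an alpha of 0.05 "with no adjustment for multiple" comparisons, and "secondary, exploratory, and safety endpoints will be reported as exploratory analyses without claims of statistical significance".

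**The concern.** An analyst who follows the SAP literally will compare raw Constant scores between the arms, although the protocol's endpoint list promises something adjusted. Because the adjustment is undefined and the test is left to be chosen as appropriate, a raw, a normalised and a model-adjusted comparison could each be defended once the data are seen.

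There is also a question of efficiency. Age, gender and the pre-operative Constant score are all collected. A comparison that ignores them leaves chance differences between the arms in the estimate and may give a wider interval than necessary. What is at stake is the clarity and precision of one secondary endpoint. Study success rests on the three co-primary endpoints and is not affected.

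**Working it through.** **Step 1: is an adjusted Constant analysis described anywhere?**

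| Place | Outcome concerned | Age or gender used? |
|---|---|---|
| Section B, Secondary Endpoints | Constant score | Yes, method not given |
| SAP, Secondary Endpoints | Constant score, unqualified | No |
| SAP, Models for Continuous Measures | Continuous baseline and secondary outcomes | No; the named tests take no covariates |
| SAP, Exploratory Analyses (regression) | Primary endpoints | Yes |
| SAP, Exploratory Analyses (time to revision) | Revision | Baseline covariates, not listed |
| Section C, Gender | Primary analysis | Gender only, conditional |

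No section supplies a covariate model for the Constant score, a normalisation formula or reference values.

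**Step 2: do the time points agree?** Section B excludes 6 weeks for this score, and a footnote to Table 1 (Screening and Follow-Up) has sites leave out the strength and motion parts at that visit. The SAP paragraph includes 6 weeks without an exception. It also names 6 months, whereas the visit schedule and the SAP's analysis windows have 3 months and no 6-month visit. The paragraph was therefore not aligned with Section B on time points either.

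**Step 3: how much precision could adjustment bring?** The plan gives no SD, effect size or power for the Constant score, so it has no figure of its own to reproduce. The number of shoulders comes from Sample Size Calculation: 112 per arm before attrition, and 112/0.85 = 131.8, that is 132 per arm.

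Unadjusted standard error of the difference = SD × sqrt(2/n).

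- n = 132: 0.1231 SD; 95% half-width 1.96 × 0.1231 = 0.241 SD
- n = 112: 0.1336 SD; 95% half-width 0.262 SD

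Let R² be the share of outcome variance that the covariates explain. It is an assumption, because the documents give no value. Ignoring lost degrees of freedom, the ratio of adjusted to unadjusted standard error is sqrt(1 − R²). With two covariates (age and gender) it is sqrt[(1 − R²)(2n − 2)/(2n − 4)]. At n = 132 and R² = 0 this is sqrt(262/260) = 1.0038.

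| R² (assumed) | sqrt(1 − R²) | Two covariates, n = 132 | Two covariates, n = 112 | 95% half-width, n = 132 (in SD) |
|---|---|---|---|---|
| 0 | 1.000 | 1.0038 | 1.0045 | 0.242 |
| 0.05 | 0.975 | 0.9784 | 0.9791 | 0.236 |
| 0.10 | 0.949 | 0.9523 | 0.9530 | 0.230 |
| 0.20 | 0.894 | 0.8979 | 0.8985 | 0.217 |
| 0.30 | 0.837 | 0.8399 | 0.8405 | 0.203 |

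The simple formula gives a standard error about 5%, 11% and 16% smaller at R² = 0.10, 0.20 and 0.30. With the two-covariate correction the reductions are about 5%, 10% and 16%. A third covariate, the pre-operative score, changes the cost at R² = 0 only to sqrt(262/259) = 1.0058, or 0.6% wider. All figures treat shoulders as independent.

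**The case against.** The strongest case against the point is that the parenthesis is attached to the score, and to the Constant score alone. If model covariates were intended, it is unclear why only one of three clinical scores would receive them. The words fit a score standardised for age and gender before analysis, and a t-test or Wilcoxon test on that score would deliver the endpoint. The SAP is a section of the same protocol, so its short list need not be read as redefining the endpoint. Scoring rules could also sit in the case report forms (Exhibit 4), which are not part of the text available here.

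Much of this stands. A reader might infer that the SAP cannot produce the protocol's endpoint; the documents do not support that, because the normalised reading is open. What remains is that the SAP neither names a normalised score nor points to a formula or reference values.

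A reader might also infer that precision is certainly lost. That is not shown either. Age and gender alone might explain almost nothing, and at R² = 0.05 the interval narrows by only about 2%. If the score is already normalised, they should explain little more. The pre-operative score could be the stronger covariate, but the protocol never promised it; adding it is an improvement, and its absence contradicts nothing in the documents.

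Finally, the consequence is small, because secondary endpoints carry no claims of significance. That limits the weight of the point but does not remove the need for a defined endpoint.

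**Conclusion.** The point holds as a gap between the endpoint list and the SAP. The adjustment is announced for the Constant score, is not defined, and is not carried into the paragraphs that govern its analysis. Followed literally, the SAP compares unadjusted scores and leaves the pre-operative value out of the comparison.

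The unadjusted comparison is valid under randomisation; the possible cost is precision. Its size rests wholly on an assumed R²: from no gain (about 0.4% wider at R² = 0 with two covariates) to a standard error about 5%, 11% or 16% smaller at R² = 0.10, 0.20 or 0.30. The upper values may need the pre-operative score as well as age and gender.

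This is a minor point. It concerns one exploratory secondary endpoint, and neither the sample size nor any co-primary conclusion changes.

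**What to change.** State in the SAP which meaning of the adjustment is intended, and make Section B, Models for Continuous Measures and the SAP's Secondary Endpoints paragraph agree.

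- **Covariate adjustment:** analyse the Constant score at each scheduled visit other than 6 weeks (3 months, 1 year, 2 years and later annual visits) by a linear model with treatment, age, gender and pre-operative Constant score. Report the adjusted investigational-minus-control difference with its confidence interval, and keep the unadjusted test as supportive.
- **Normalised score:** name that score in the SAP's Secondary Endpoints paragraph, give its formula and reference values, and keep its pre-operative value as a covariate.
- **Time points:** reconcile the 6-week entry (for the Constant score) and the 6-month entry in that paragraph with Section B, Table 1 and the visit schedule.

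The cost is SAP wording and one regression per visit. Age, gender and the pre-operative Constant score are already collected, so no visit, form or sample size changes. The choice should be fixed before outcome data are compared by arm.
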